5.2 Exclusion Criteria

Yes/No (Response of “yes” = subject ineligible)

5.2.1 Known brain or visceral metastases other than lymph nodes (defined in section 5.1.6) as defined by CT, MRI, or other molecular imaging (e.g., fluciclovine PET/CT or PSMA PET/CT scan or other per PI discretion).

5.2.2 Patients actively receiving hormone therapy for prostate cancer. Patients may have received hormone therapy previously but must have documented non-castrate levels of testosterone (>50 ng/dL).

5.2.3 Prior or concurrent malignancy whose natural history or treatment, in the opinion of the enrolling investigator, may have the potential to interfere with the safety or efficacy assessment of the investigational treatment protocol of this study.

5.2.4 _____ Use of finasteride within 30 days prior to initiation of therapy. Baseline PSA should not be obtained prior to 30 days after stopping finasteride.

5.2.5 _____ Use of dutasteride within 90 days prior to initiation of therapy. Baseline PSA should not be obtained prior to 90 days after stopping dutasteride.

5.2.6 _____ Use of any prohibited therapy noted in 6.3.2.

5.2.7 _____ Active, uncontrolled, significant intercurrent or recent illness including, but not limited to, the following conditions:

- Cardiovascular disorders:
 - Congestive heart failure New York Heart Association Class 3 or 4, unstable angina pectoris, serious cardiac arrhythmias.
 - Uncontrolled hypertension defined as sustained blood pressure (BP) > 150 mm Hg systolic or > 100 mm Hg diastolic despite optimal antihypertensive treatment.
 - Stroke (including transient ischemic attack [TIA]), myocardial infarction (MI), or other ischemic event, or thromboembolic event (e.g., deep venous thrombosis, pulmonary embolism) within 6 months before first dose.
- Acute bacterial or fungal infection requiring intravenous antibiotics at the time of registration
- Chronic obstructive pulmonary disease exacerbation or other respiratory illness requiring hospitalization or precluding study therapy at the time of registration or within 30 days of registration.
- Hepatic insufficiency resulting in clinical jaundice and/or coagulation defects;

I certify that this subject meets all inclusion and exclusion criteria for enrollment onto this study.

Investigator Signature

Date

Time

5.3 Recruitment Strategies

Potential subjects will be identified by Investigators in the setting of their outpatient clinics.

6 TREATMENT GUIDELINES

6.1 Subjects with Bone Metastases Only

Bone metastases will be treated with stereotactic body or hypofractionated radiation per institutional standard of care guidelines. The investigator will select the type of radiation based on the nature of the disease.

Following completion of radiation treatment subjects will move on to the follow-up phase of the study as described in Section 9.3.

6.1.1 Dose Specification

All subjects will receive stereotactic body or hypofractionated radiation to sites of bone disease seen on imaging studies. Radiation will be administered per institutional standard of care which is commonly 16-44 Gy in 1-6 fractions, using any one of the isoequivalent radiation regimens (based on the linear quadratic model with $EQD2 \geq 60$ and an alpha/beta ratio for prostate cancer=2) to allow the radiation oncologist flexibility to deliver an ablative dose while sparing normal tissues depending on tumor location. In cases where radiation is administered outside of these parameters, prior approval will be obtained from the PI and medical monitor.

6.1.2 Target Localization

This study requires the use of IGRT, a computer assisted process that uses imaging devices that generate a series of coordinates for shifting the patient support system in three orthogonal directions (sometimes including rotational changes) to position the treatment beams relative to target regions. The allowed technologies are as follows: cone-beam CT (CBCT) using either a specially mounted kV imaging head or the MV treatment beam with an opposed electronic imaging panel, dual fixed-position in-room kV imaging systems that are orthogonal or near orthogonal, an in-room standard diagnostic CT scanner that is geometrically linked to the treatment unit, and the tomotherapy approach.

Simple portal imaging approaches that do not use computer assistance are not considered to be suitable for this study.

When the treatment equipment is not equipped with any device that allows direct visualization of anatomical structures using the treatment beam, the recommendations of AAPM Task Group Report 142 for testing the coincidence of the imaging and treatment reference points must be implemented. For example, verification of treatment and imaging isocenter coincidence must be performed routinely for the CyberKnife, Tomotherapy units as well as any BrainLab equipment that does not include an electronic portal imaging device (EPID) that intercepts the treatment beam.

6.1.3 Target Volume Definition

Non-Spinal Osseous Sites

GTV = gross tumor apparent on CT or MRI, or other molecular imaging (e.g., fluciclovine PET/CT or PSMA PET/CT scan or other per PI discretion).

CTV = GTV.

PTV will be uniform expansion of 3-5 mm.

Spinal Osseous Sites

[figure not shown]
GTV = gross tumor apparent on CT or MRI, or other molecular imaging (e.g., fluciclovine PET/CT or PSMA PET/CT scan or other per PI discretion). The GTV will include 1 of the following (as illustrated in Figure 6.1):

- a. The vertebral body only OR
- b. The vertebral body and pedicle OR
- c. Posterior elements only

CTV = GTV.

PTV will be as per RTOG 0631.

Figure 6.1. Diagram of Spine Metastases and Target Volumes

6.1.4 Planning Techniques

6.1.4.1 General Considerations

A variety of planning techniques can be used to deliver SBRT for each metastasis. General guidelines include the following:

- Multiple coplanar or non-coplanar beam arrangements are acceptable.
- Typically 7-13 static radiation beams with equal weighting are used. It is recommended that at least 10 beams be used when possible.
- A minimum field dimension of 3 cm should be observed treating small metastases.
- Dynamic conformal arcs are acceptable. It is recommended that arcs span at least 340 degrees.
- For non-IMRT or dose painting techniques, the conformal field aperture size and shape should correspond nearly identically to the projection of the PTV along a beam's eye view (i.e., no additional "margin" for dose buildup at the edges of the blocks or MLC jaws beyond the PTV). The only exception will be when observing the minimum field dimension of 3 cm when treating small lesions.
- The prescription isodose line covering 95% the PTV will generally be 80-90% but may range from 60-90% where the maximum dose is 100%. As a result, a "hotspot" will exist

within the PTV that is equal to the prescription dose divided by the prescription isodose line (i.e., $45\text{Gy}/0.6 = 75\text{Gy}$ when 45Gy is prescribed to the 60% isodose).

- Doses higher than the prescription isodose (i.e., hotspots) should be manipulated to occur within the target.

6.1.4.2 Dose calculations

All dose distributions shall include corrections for tissue heterogeneities.

6.1.4.3 Normalization

The treatment plan should be initially normalized such that 100% corresponds to the maximum dose within the PTV (MAXPTV). While this point will typically correspond to the PTV center of mass, it can be located elsewhere within the PTV.

1. **Prescription Isodose Surface Coverage:** The prescription isodose surface will be chosen such that 95% of the target volume (PTV) is conformally covered by the prescription isodose surface. Doses less than 95% of the prescription dose are restricted to the outside edges of the PTV. The prescription isodose surface selected MUST be $\geq 60\%$ and $\leq 90\%$ of the dose maximum within the PTV (MAXPTV). The MAXPTV corresponds to the normalization point (100%) of the plan as noted above.
2. **Target Dose Heterogeneity:** Rather than prioritizing target dose homogeneity, SBRT treatment planning prioritizes adequate minimum target coverage and rapid dose fall-off gradients outside of the target. Hot spots within targets are generally accepted without consequence since targets are mostly tumor. The only exception is when the hotspot within the PTV also intersects an OAR.
3. **Critical Organ Doses:** Respect all critical organ dose-volume limits as Described by either: The report of AAPM Task Group 101, the NRG BR-001 protocol, or the RTOG 0631 treatment protocol.
4. **High-Dose Spillage:**
 - a. **Location:** Any dose $> 105\%$ of the prescription dose should occur within the PTV and not within the normal tissues outside the PTV.
 - b. **Volume:** Acceptable isodose distributions should be as conformal as possible. To this end the ratio of prescription isodose volume to PTV should be as small as possible.
 - i. The ratio of the prescription isodose volume to the PTV volume should be < 1.2 . Acceptable variations include a ratio of 1.2-1.5. Ratios above 1.5 will be considered unacceptable variations. The prescription line for each lesion will be contoured for calculation of this ratio. The prescription line will be labelled as V_5000 with the 5000 changing to reflect the prescription dose in cGy.
 - ii. Guidelines for the ratio of the 50% prescription isodose volume to the PTV volume (R50%) and for the maximum dose at 2 cm (D2cm) from the PTV are given in Table 6.1. Because it may become more difficult to restrict the 50% isodose volume when dose is summed from treatment of multiple metastases, this ratio should be evaluated for dose calculated for a single metastasis (i.e., not for composite dose). This is acceptable as long as normal tissue constraints are met.

- iii. Elliptically shaped metastases as well as extremity metastases may not meet these guidelines. This is acceptable as long as normal tissue constraints are respected.
- iv. These criteria will not be required in treating very small tumors (< 2.5 cm axial GTV dimension or < 1.5 cm craniocaudal GTV dimension) in which the required minimum field size of 3 cm results in the inability to meet a conformity ratio of 1.5.

Table 6.1: Guidelines for the Ratio of the 50% Prescription Isodose Volume to the PTV Volume (R50%) and for the Maximum Dose at 2 cm (D2cm) from the PTV

PTV Volume (cc)	Ratio of 50% Prescription Isodose Volume to PTV Volume, R50%	Maximum Dose at 2cm (D2cm) from PTV in any direction as % of Prescribed Dose
1.8	< 7.5	< 57.0
3.8	< 6.5	< 57.0
7.4	< 6.0	< 58.0
13.2	< 5.8	< 58.0
22.0	< 5.5	< 63.0
34.0	< 5.3	< 68.0
50.0	< 5.0	< 77.0
70.0	< 4.8	< 86.0
95.0	< 4.4	< 89.0
126.0	< 4.0	< 91.0
163.0	< 3.7	< 94.0

NOTE: For values of PTV dimension or volume not specified, linear interpolation between table entries is required.

NOTE: For tumors within 2 cm of the skin, it may be difficult to meet the values for D2cm and R50%. In these cases, these criteria will not be used.

6.2 Subjects with Nodal Metastases (With or Without Bone Metastases)

Subjects with nodal metastases will initially be treated with salvage resection of their nodal disease followed, as needed, by treatment of their bone metastases. In some cases and at the discretion of the investigator (e.g., painful bone lesions), treatment of the bone lesions can take place before nodal resection.

6.2.1 Oligometastasectomy

Subjects with pelvic or para-aortic lymph node metastases will undergo surgical dissection. Treatment will cover the bilateral nodal group identified by molecular imaging (e.g., fluciclovine PET/CT or PSMA PET/CT scan or other per PI discretion), and one level above and one level below any identified nodal region.

Nodal groups from distal to proximal include: 1) Obturator fossa, 2) External iliac, 3) Common iliac, 4) Aortic-below IMA, 5) Aortic-above IMA.

Metastases to superficial inguinal nodes will also be considered for surgical dissection in which cases both a superficial inguinal lymph node dissection and pelvic lymph node (obturator fossa and external iliac nodes) dissection will be performed.

For subjects who were treated with definitive radiotherapy pre-study and have a positive TRUS biopsy at baseline, or less than or equal to a year before study enrollment, salvage prostatectomy will be performed along with the procedure described above (unless salvage radiotherapy is indicated as described in Section 3.2.1).

6.2.2 Radiotherapy to Bone Metastases (As Applicable)

Following recovery from their nodal resection, subjects with bone metastases will be treated with radiotherapy as described above in Section 6.1.

6.2.3 Adjuvant Nodal Radiation Therapy

Within 4 months following completion of salvage therapy (defined as the combination of oligometastasectomy and/or bone radiation) and depending on PSA response as well as previous treatment, patients may receive adjuvant nodal IMRT as highlighted in Figure 2 and as described below.

6.2.3.1 Subjects whose PSA declines to 0 following resection

This will be considered a complete PSA response (PSA CR) and no further treatment will be required. Subjects will move on to the follow-up phase of the study as described in Section 9.3.

6.2.3.2 Subjects whose PSA declines by $\geq 1/3$ but remains > 0.2 ng/mL

Following confirmation of the lack of PSA response (2 consecutive PSA values obtained at least 3 weeks apart which have decreased from the pre-resection value by $\geq 1/3$ yet remain > 0.2 ng/mL, considered a partial PSA response or PSA PR), subjects will receive IMRT based on their previous treatment history:

Option 1

- Subjects who have undergone prior salvage/adjuvant radiotherapy to the pelvis (with or without treatment of para-aortic lymph nodes)

OR

- Subjects who have undergone prior prostate radiotherapy with pelvic/nodal irradiation
 - Ipsilateral involved-field image-guided IMRT with boost to any identifiable lesions.
 - Dose will be 45 Gy in 25 fractions
 - Simultaneous integrated boost to gross target volumes must be ≥ 76 Gy in total equieffective dose (EQD2)

Option 2

- Subjects who have undergone prior prostate radiotherapy without pelvic/nodal irradiation

OR

- Subjects who have undergone prior prostatectomy without adjuvant/salvage radiotherapy:
- Bilateral pelvic image-guided IMRT with boost to any identifiable lesions.
 - Inferior field border functioned immediately above the previously treated field to 50.4 Gy
 - Simultaneous integrated boost to gross target volumes must be \geq 76 Gy in total equieffective dose (EQD2)

Following adjuvant radiation therapy, subjects will move on to the follow-up phase of the study as described in Section 9.3.

6.2.3.3 Subjects whose PSA declines by < 1/3

This will be considered a treatment failure (PSA response failure), no adjuvant therapy will be given. Subjects will enter the follow-up period until diagnosis of metastatic disease and will not receive any further treatment.

6.3 Concomitant Medications and Therapies

6.3.1 Allowed Therapy

Any medication which is considered necessary for a subject's welfare is permitted and may be given at the discretion of the investigator. Medications for treatment of underlying disease and symptomatic treatment of adverse events are permitted. Exceptions are listed in the section below.

6.3.2 Prohibited Therapy

- Concurrent anti-cancer therapy (chemotherapy, androgen deprivation therapy, immunotherapy, biologic therapy, or tumor embolization) and external beam radiation other than those specified in this protocol.
- Concurrent use of another investigational drug or device therapy (i.e., outside of study treatment) during, or within 4 weeks of trial entry (signing of the informed consent form).
- Major surgery within 30 days prior to enrollment.

6.4 Duration of Therapy

6.4.1 Criteria for the Discontinuation of Treatment (“Off Treatment”)

Patients may withdraw from treatment or the study overall at any time at their own request, or they may be withdrawn at the discretion of the Investigator for safety, behavioral reasons, or the inability of the patient to comply with the protocol-required schedule of study visits or procedures.

In addition to the drug-specific discontinuation criteria listed in Dose Modification Section, the following will result in treatment discontinuation:

- Adverse events or intercurrent illness that in the opinion of the investigator warrants the subject's withdrawal from study treatment

- The subject or legally authorized representative requests to discontinue the study treatment and/or study procedures
- Salvage treatment failure defined as radiographic progression per PCWG3 criteria OR RECIST 1.1. Patients taken off treatment for treatment failure will continue to be followed for toxicity assessments only every 6 months.
- Failure to initiate adjuvant radiotherapy within 4 months of completion of salvage therapy (oligometastasectomy and/or bone radiotherapy).
- Patient refused further treatment
- Significant noncompliance with the protocol schedule or treatment administration in the opinion of the investigator
- Clinical deterioration that, in the opinion of the investigator, increases the risk to the subject

Surgery may be aborted if unforeseen complications arise.

Radiation therapy courses may be shortened in case of RTOG Grade III-IV or persistent (≥ 2 weeks) Grade II toxicities. Continuation of treatment during Grade III toxicities may be allowed if the patient is benefiting as assessed by the treating investigator.

6.4.2 Criteria for the Discontinuation of Study (“Off Study”)

Subjects will be taken off study for the following:

- Study terminated by investigator sponsor
- Completed study follow-up period
- Participant or legally authorized representative requests to be fully withdrawn from the study
- If, in the investigator's opinion, continuation of the trial would be harmful to the subject's well-being.
- Development of an intercurrent illness or situation which would, in the judgment of the investigator, significantly affect assessments of clinical status and trial endpoints.
- Initiation of new anti-cancer therapy
- Subject is lost to follow-up
- Death
- Screen failure

7 TOXICITIES AND DOSEAGE MODIFICATION

This study will utilize the CTCAE (NCI Common Terminology Criteria for Adverse Events) Version 5.0 for adverse event and serious adverse event reporting. Radiation toxicities will be graded according to the Radiation Therapy Oncology Group (RTOG) toxicity grading system (Appendix A) and surgical complications will be graded according to the Clavien-Dindo classification (Appendix B).

7.1 Dose Modifications and Guidelines for Adverse Event Management for Radiotherapy

7.1.1 Dose Modifications

In the event of a clinically significant CTCAE v5 adverse event \geq grade 3, which is felt to be at least possibly related to radiation therapy, treatment will be discontinued. Treatment related adverse events \leq grade 2 may result in a reduction in the dose of radiation therapy if the treating physician feels that further radiation would be likely to exacerbate harm to the patient.

Radiation therapy courses may be shortened in case of RTOG Grade III-IV or persistent (\geq 2 weeks) Grade II toxicities. Continuation of treatment during Grade III toxicities may be allowed if the patient is benefiting as assessed by the treating investigator.

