^{xvii} Optional blood draws may be performed prior to starting salvage therapy, at the next standard of care follow up visit after completion of salvage therapy, and at the time of confirmed PSA progression or radiological progression. See Section 14.3 for details.

^{xviii} After completion of salvage treatment, optional blood will only be collected once at time of confirmed disease progression.

^{xix} Optional archival tissue may be collected at baseline for all subjects for whom it is available. Archival tissue slides should not be cut until requested from the Central Lab. Lack of archival tissue will not be exclusionary.

^{xx} Optional fresh tissue may be collected prior to starting salvage therapy during the TRUS biopsy (if performed) and at the time of oligometastasectomy or prostatectomy (if indicated and if available after SOC tissue collection). See Section 14.1 and 14.2 for details.

^{xxi} Quality of life (QOL) questionnaires (FACT-P and Expanded Prostate Cancer Index Composite EPIC-26) will be collected prior to starting salvage therapy, at the Response Assessment Visit, and at each follow-up visits. See Appendices C and D.

^{xxii}To be performed at the Response Assessment Visit and at each follow-up visits. See Appendix A

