All adverse events will be treated appropriately. Such treatment may include changes in study salvage treatment as listed in the dose modification section of this protocol (see section 8 for guidance). Once an adverse event is detected, it should be followed until its resolution, and assessment should be made at each visit (or more frequently, if necessary) of any changes in severity, the suspected relationship to the study salvage treatment, the interventions required to treat it, and the outcome.

All adverse events will be immediately recorded in the subject research chart.

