15.5.2 Serious Adverse Event (SAE)

Information about all serious adverse events will be collected and recorded. A serious adverse event is an undesirable sign, symptom or medical condition which:

- Is fatal or life-threatening
- Results in persistent or significant disability/incapacity
- Is medically significant, i.e., defined as an event that jeopardizes the subject or may require medical or surgical intervention to prevent one of the outcomes listed above
- Causes congenital anomaly or birth defect
- Requires subject hospitalization or prolongation of existing hospitalization, unless hospitalization is for:
 - Routine treatment or monitoring of the studied indication, not associated with any deterioration in condition (procedures such as central line placements, paracentesis, pain control)
 - Elective or pre-planned treatment for a pre-existing condition that is unrelated to the indication under study and has not worsened since the start of study salvage treatment
 - Treatment on an emergency outpatient basis for an event not fulfilling any of the definitions of a SAE given above and not resulting in hospital admission
 - Social reasons and respite care in the absence of any deterioration in the subject's general condition

Collection of serious adverse events will begin at the time of salvage treatment and end 1 year after the last dose of study treatment or until a new cancer treatment is initiated, whichever happens the soonest.

Any death from any cause while a subject is receiving treatment on this protocol or up to 365 days after the last dose of protocol treatment will be reported. Any death which occurs up to 3 years after protocol treatment has ended but which is felt to be treatment related, must be reported.

Toxicities which fall within the definitions listed above must be reported as an SAE regardless if they are felt to be treatment related or not. Toxicities unrelated to treatment that do NOT fall within the definitions above, must simply be documented as AEs in the subject research chart.

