Appendix A – Radiation Therapy Oncology Group (RTOG) toxicity grading system

Patient ID: _____

Date: _____

Time point: _____

0	1	2	3	4	5
No symptoms	Minor symptoms requiring no treatment	Symptoms responding to simple outpatient management, lifestyle (performance status) not affected	Distressing symptoms altering the patient's lifestyle (performance status) Hospitalization for diagnosis or minor surgical intervention (such as urethral dilation) may be required	Major surgical intervention (such as laparotomy, colostomy, cystectomy) or prolonged hospitalization required	Fatal complications

Physician signature: _____

Date: _____

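### Section 7.1.1 requires radiotherapy to stop for a related, clinically significant grade 3 event, then allows it to continue during Grade III toxicity, and no text says which rule governs

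*Combined protocol and SAP*

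**What the plan says.** Section 7.1.1 has two paragraphs on when radiotherapy stops.

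- The first is mandatory. It covers a clinically significant CTCAE v5 event of grade 3 or higher "which is felt to be at least possibly related to radiation therapy, treatment will be discontinued". It adds that related events of grade 2 or lower may lead to a dose reduction if the physician expects more radiation to worsen the harm.
- The second is permissive. A course may be shortened for RTOG Grade III-IV toxicity, or for Grade II toxicity lasting two weeks or more. It ends: "Continuation of treatment during Grade III toxicities may be allowed if the patient is benefiting as assessed by the treating investigator". This last sentence names no grading scale.

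Section 6.4.1 repeats the second paragraph in full. Its list of off-treatment reasons opens with "In addition to the drug-specific discontinuation criteria listed in Dose Modification Section, the following will result in treatment discontinuation".

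Section 7 uses CTCAE v5.0 for reporting adverse events and adds: "Radiation toxicities will be graded according to the Radiation Therapy Oncology Group (RTOG) toxicity grading system". One radiation toxicity can therefore carry a grade on each scale.

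Section 15.5.1 says that treatment may be changed "as listed in the dose modification section of this protocol (see section 8 for guidance". Section 8 is the study calendar; the dose modification rule is in 7.1.1.

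**The concern.** A grade 3 radiation toxicity that is clinically significant and possibly related meets the conditions of both paragraphs. The first says stop. The second lets the investigator carry on. The choice decides whether a patient with a severe toxicity receives more radiation, including under Option 1 of Section 6.2.3.2, where adjuvant IMRT is given after earlier pelvic or nodal irradiation.

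It also matters for oversight. Section 15.9 defines a deviation as a departure from the approved treatment plan, and Section 15.4 has the DSMC review deviations. A monitor who finds that radiotherapy continued through such an event could classify it as a deviation under one paragraph and as permitted under the other.

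**Working it through.** This is a question of wording; no arithmetic applies. The check sets the two paragraphs of 7.1.1 side by side, then looks for text elsewhere that ranks them.

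**Step 1: where they collide.** Suppose the event has the same grade number on both scales and occurs before the last fraction.

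| Event during a course | First paragraph (CTCAE) | Second paragraph (RTOG named for shortening) |
|---|---|---|
| Grade 4, related, clinically significant | Must stop | May be shortened; no permission to continue |
| Grade 3, related, clinically significant | Must stop | May be shortened; may continue if benefiting |
| Grade 3, unrelated or not clinically significant | No stop required | May be shortened; may continue if benefiting |
| Grade 2, lasting two weeks or more | Dose may be reduced if related | May be shortened |

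Only the second row contains opposite instructions. Stopping satisfies both paragraphs there, because the second only permits. Continuing breaks the first and is allowed by the second.

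**Step 2: do the qualifiers separate the rules?** The first turns on clinical significance and relatedness; the second turns on benefit. A patient can be judged to benefit while having a related, clinically significant event, so the conditions overlap.

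**Step 3: do the two scales separate them?** No text maps RTOG grades to CTCAE grades, and the continuation sentence names neither. Section 9.2 requires CTCAE and Clavien-Dindo assessment at every clinic visit once treatment has begun. The RTOG evaluation is "To be performed at the Response Assessment Visit and at each follow-up visits" in the Arm C calendar, and the Arm A and B calendars say the same. The grade scheduled during a course is therefore CTCAE, the scale of the mandatory rule, although Section 7 assigns radiation toxicity to RTOG.

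**Step 4: does discontinued mean only paused?** The action list in 15.5.1 distinguishes temporary interruption from permanent discontinuation, and 6.4.1 deals with going off treatment. Neither supports reading the first paragraph as a pause.

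**Step 5: does another section decide?**

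- 6.4.1 repeats the permissive paragraph and does not restate the mandatory rule or rank the two.
- 7.1.2 leaves management of radiation adverse events to the radiation oncologist and institutional standards. It does not mention stopping; read as an override, it would leave the first paragraph of 7.1.1 without effect.
- 15.5.1 sends the reader to the calendar, which contains no dose rule.

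No section supplies an exception or an order of precedence.

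**The case against.** The strongest reply is that a coherent reading exists. The continuation sentence closes the same short subsection, is limited to Grade III and has its own condition. Read as specific over general, it gives: stop at grade 3, unless the investigator judges benefit. That may well be the intent. It is not written, however. As an implied exception it also has no documentation step, whereas Section 6.1.1 requires prior approval from the PI and medical monitor for bone doses outside the stated parameters. No calendar schedules PSA or disease imaging during a course, so benefit would rest on unrecorded judgement.

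It can also be said that the mandatory rule already depends on judgement (clinical significance and relatedness), that the trial has a single centre, and that the DSMC reviews SAEs monthly and on-treatment toxicities quarterly. All of that stands. It limits how often the ambiguity will matter, and a clearer rule will still leave those two judgements open. It does not reconcile the two sentences.

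A reader might infer that 6.4.1 settles the matter by making the 7.1.1 stop an off-treatment criterion. The documents do not support that firmly: the reference is to drug-specific criteria, and the treatment here is surgery and radiotherapy.

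**Conclusion.** The conflict is real and should be corrected. For a related, clinically significant grade 3 event during radiotherapy, the plan requires a stop and permits continuation, and cannot be followed as written. The conclusion rests on the text alone, assuming only that one event can meet both paragraphs.

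Its size cannot be given, and four stronger readings are not supported:

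- **A number of affected subjects.** The Background reports no significant toxicities in a 43-subject SBRT study. This cannot be turned into a rate for all 20 subjects: Arm B receives no bone radiotherapy, the statement is not limited to toxicity arising during a course, a single-fraction course cannot raise the question, and nothing is reported for adjuvant IMRT.
- **Bias in the primary endpoint.** Stopping early could decide whether an Arm A or C subject reaches the 70% of planned radiation required by 11.2.2 or is replaced. No event rate links this to the response estimate, and how the 70% is counted is a separate question.
- **A breach of SAE rules.** RTOG Grade 3 can involve hospitalization, but SAE status triggers no radiotherapy stop in this protocol.
- **Permission to treat through Grade IV.** The second paragraph says only that a course may be shortened there.

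Toxicity data are not lost, since 15.5.1 records the CTCAE grade and the action taken.

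**What to change.** State one stopping rule in CTCAE v5 grades, with identical wording in 7.1.1 and 6.4.1:

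- Grade 4 or higher, related and clinically significant: mandatory stop.
- Grade 3, related and clinically significant: stop, unless continuation is written as an explicit exception with the investigator's benefit-risk reason documented. The alternative is to delete the continuation sentence. Which to choose is for the investigators.
- Grade 2 lasting two weeks or more: the course may be shortened.
- Grade 2 or lower: keep the existing dose-reduction provision.

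Amend Section 7 to say that CTCAE governs on-treatment stopping and that RTOG is used for the evaluations already scheduled at Response Assessment and follow-up. Correct the reference in 15.5.1 from section 8 to 7.1.1.

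The cost is a wording amendment to four places, which needs IRB approval under 15.8, and slightly less investigator discretion at grade 3. If the exception is kept, each use needs a recorded reason. No visit or analysis is added.
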